2.2.3 Baseline phase

The baseline period is specific to each user. It starts the day the user has been positively assessed for eligibility (passes eligibility criteria). This can be any day within the recruitment period. It ends when the recruitment window closes:

- Participants cannot complete baselining if they do not respond to at least one 24-hour dietary recall using Intake24⁸. The second intake24 is optional; users are encouraged to complete the second one within 3 days – this 3-day window is intended to streamline the onboarding experience for participants and provide a sufficient time period for participants to complete a second Intake24, while reducing the risk that the participants' baselining period is unduly protracted (which may add to abandonment-risk).
 
- Participants cannot complete baselining if they do not connect a wearable device; the (physical activity) challenges require at least 5 days of data⁹ during the baseline period. A day of data constitutes a day in which at least one step is registered. To calculate the baseline physical activity (PA), the first day is excluded as it is assumed that the data is partial only on the first day.
- Participants answer a food frequency questionnaire which will be used to create personal diet challenges (please see HUL's intervention design plan for more detail).

Their baseline period ends when this happens, and they enter randomisation

During this time:

- Participants indicate whether they need a wearable device and they receive it via mail;
- Participants may complete optional survey instruments (mental health, how they heard about the programme, education survey, motivations to change, disability survey);
- Participants provide the baseline data that HUL requires to fine-tune and personalise the incentive scheme (see the design protocol developed by HUL for more details);
- Participants provide the baseline outcome data that BIT requires for evaluation:
 - At least one Intake24 recall, to measure baseline dietary intakes;

⁸ Intake24 is a web-based self-completed 24-hour dietary recall system and has been widely used in national food and nutrition surveys.

⁹ Users exercise minutes and heart rate (HR) data are not required during the baseline period.

- Physical activity data for 5 days by the wearable device¹⁰;
- Sleep quality data and mental health (note: providing these data is not a prerequisite for entering randomisation)
- Motivation to increase PA and to improve dietary intake

Collecting outcome measures before exposing participants to the intervention will allow us to control for baseline average dietary intake and physical activity in the analysis (increasing precision of the treatment effect estimates through reducing pre-intervention between-group variance). See the data transfer supplement for the full list of data to be collected and transferred between HUL and BIT.

A significant risk for the success of the evaluation is if not enough participants successfully enter the trial (measured as entering randomisation), either because the target recruitment number is not met, or because attrition during the baseline phase is higher than estimated by HUL.¹¹ To address this, BIT and HUL have decided on the following mitigation strategies (more details are provided by HUL in their acquisition and mitigation plan):

Decision - When	Focus	What	Team responsible
Before the trial	Recruitment and baseline phase	BIT adopted a conservative approach to power calculations to determine the required sample size (pre-post correlation of outcome measures, distribution of household sizes that are expected to sign up, proportion of people that are expected to sign up within each household).	BIT
Before the trial	Recruitment	Providing a free wearable device to all participants who do not have one (including those in the control group), which might incentivise people to enrol into the study. This will help to recruit participants within the short timelines available. ¹²	HUL

Table 2	2. M	itigation	strategies

¹⁰ Note that a minimum of 4 valid days of physical activity data are required for inclusion in the evaluation. The first of the 5 days of data collected at baseline is therefore excluded from the evaluation as it is assumed to be a partial day. A valid day of data is one for which there is at least 6 hours of device wear time. This is explained in section 2.6 Data collection, management, and analysis ¹¹ BIT and HUL acknowledge that the risk of attracting too many users is also present. In this case, HUL will collect the same data as currently proposed during onboarding /registration (i.e. email, name, DOB, BMI, consent, gender etc) from the 'extra' users who will be invited to take part in the pilot. The app will limit the total number of registered users to 31,500. Once this number has been reached, users will see a message before they sign up, alerting them that the pilot is full and no more registrations are permitted, nor data captured.

¹² For the aim of the evaluation we do not consider the wearable a financial incentive (as part of the scheme), as the wearables will be provided to both the intervention and control group primarily to measure physical activity. Providing the wearable to both the intervention and control group will allow us to isolate the effects of providing financial rewards that are contingent on behaviour change. However, we acknowledge that users' behaviour will be affected by the presence of a wearable device.

Before the trial	Recruitment	Testing and fine-tuning of recruitment materials via UX research and online RCTs.	HUL, BIT supported with one online RCT
Before the trial	Baseline phase	Testing and fine-tuning the onboarding phase via UX and acceptability user testing research. This includes minimising the number of questions users are asked during the onboarding phase (for the evaluation and the fine-tuning of the scheme).	HUL
Before the trial	Baseline phase	Make data collection easy and attractive: (i) Adopt reminders to encourage data collection; (ii) Display the Intake24 survey link prominently on the 'to-do' list dashboard of the app when users open it so they'll see it every time they open the app regardless of the prompt; (iii) Encourage two recalls of Intake24 and wearing the device with a small payment (£5 as points); (iv) Provide feedback after each Intake24 recall	HUL
Before the trial (triggered)	Baseline phase	Extend the baseline phase to up to 2 weeks if users are slow to provide their data	HUL
Before the trial	Onboarding phase	Adopt a flexible onboarding period for 'slow onboarding users' if needed - ideally a user completes screening in 2 or 3 weeks (nudged to do so), but if they don't, they enter the trial (randomisation) when they have met the baseline criteria, rather than after a predetermined window of time.	HUL
		The latest calendar date that a user can complete onboarding (pass screening) is the last day of the recruitment window.	
During the trial	Recruitment	Extend the recruitment period beyond 6 weeks if necessary	HUL
During the trial (triggered at M5)	Trial period	Make data collection attractive: Consider encouraging wearing and syncing the wearable device with the app in the crucial data collection weeks at m3 and m5 with a small payment (£10), if attrition is deemed relatively too high ¹³ at the data collection point at m1 and m3.	HUL
During the trial (triggered at M3 and M5)	Trial period	Make data collection attractive: Consider encouraging filling in Intake24 at m3 and m5 with a larger payment (£10), if attrition is	HUL

¹³ We consider the attrition too high if the number of users not providing their data 10% smaller than expected at the start of the 1 month mark (see Table 6 for the expected attrition at different trial stages).

		deemed relatively too high ¹⁴ at the data collection point at m1. At m5 - for PA, users will receive £5 for syncing their fitness tracker (any amount of data > 0) during weeks 21 and 22 - up to 2 times so they can earn up to an extra £10.	
During the trial (triggered)	Trial period	Extend the data collection window from 2 to 3 weeks (21 days) at m3 and m5 for all measures (i.e. Intake24, steps, WHO5, sleep and weight)	HUL
During the trial	Trial period	Pull data collection forward. Change M5 data collection window to start earlier i.e. during the 20th week (day 134 to day 155).	HUL
After the trial	Recruitment and baseline phase	Shift the focus of the evaluation to a shorter follow-up (e.g. after 3 months of treatment instead of 5 months). If the sample size at 5m is less than 80% of the total sample size (n = 4,200) that the trial requires in order to detect a minimum effect size for primary outcomes (see Table 7 for details), we will use data from the 3m mark instead of the 5m mark in the analysis. ¹⁵	BIT

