2.6.2 Data quality management

We will seek to obtain high-quality **physical activity data** with two strategies:

- **During data collection.** Participants will be nudged to wear and synchronise the device throughout the trial period to maximise the data fidelity of MVPA mins and steps count and to minimise missingness.
- **Before analysis.** Based on univariate analysis, we will search for and exclude or replace outlier values. We are aware that due to some technical glitches, participants' physical activity data may exceed plausible boundaries (e.g. more than 1440 minutes of MVPA per day, or more than 3 million steps per day). To mitigate the influence of those outliers, we will exclude the implausible records and apply further boundary rules (excluding observations that are below the 2.5th or above the 97.5th percentiles) to ensure data fidelity. BIT will also inspect PA sample data after trial launch and refine the above criteria to handle outliers if necessary (see section 2.6.3.2 for details).

Likewise, the quality of **diet data** will also be managed at two stages: during data collection and before data analysis:

- **During data collection.** Intake24 includes automatic checks and nudges to rule out implausible inputs (e.g. portion size, time gap between meals).
- Before analysis.
 - (i) Firstly, we will exclude administrations satisfying any of the following conditions (these conditions were used in the National Diet and Nutrition Survey (NDNS)):
 - Fewer than 10 food items in a recall
 - 3 or fewer eating occasions in a recall (this includes occasions when a participant reports consuming only a drink without food)
 - Completion time of under 3 minutes
 - Total energy intake less than 400kcal or more than 4,000kcal and the individual had not stated that they consumed "less than usual", "more than usual", or that they were on a weight gain or weight loss diet
 - (ii) After doing this, we will inspect the distributions of the dietary outcomes and compare that against the mean level and standard deviation of UK adults' food and macro-nutrients consumption. We will then exclude values below the 1st or above the 99th percentile, by gender.

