2.6.3.5 Analytical strategy for the primary analysis

The primary outcomes for physical activity are **MVPA minutes per day and daily** steps at 5 months into the trial (week 21).

We will test for differences between the pooled treatment arms and the control arm five months after randomisation using an intention-to-treat approach and a **linear mixed model (panel regression with random effects)** appropriate for clustered data with repeated measurements, in line with methodology adopted by studies with similar designs^{58,59}. As part of the analytical strategy, we will control for the individual characteristics of age, sex, ethnicity, education, BMI at baseline, the brand of wearable.

The general equation for estimating the model is as follows:

(1)
$$y_{ijd} = \alpha + \beta Treatment_j + \gamma_d + \gamma_W week_{ijd} + \gamma_B baseline_{ijd} + \gamma_M missing. baseline_{ijd} + ... \gamma_X X_{ij} + \delta_{cj} + \delta_{pij} + u_{ijd}$$

 $\delta_{cj} \sim N(0, \sigma_c^2); \ \delta_{pij} \sim N(0, \sigma_p^2) for all i, j; \ u_{ijt} \sim N(0, \sigma_u^2) for all i, j, d$

where:

• y_{iid} is the daily MVPA minutes for participant *i* within household *j* on day *d*;

⁵⁸ Harkins, K. A., Kullgren, J. T., Bellamy, S. L., Karlawish, J., & Glanz, K. (2017). A Trial of Financial and Social Incentives to Increase Older Adults' Walking. *American Journal of Preventive Medicine*, *52*(5), e123–e130. doi: 10.1016/j.amepre.2016.11.011

⁵⁹ Finkelstein, E. A., Haaland, B. A., Bilger, M., Sahasranaman, A., Sloan, R. A., Nang, E. E. K., & Evenson, K. R. (2016). Effectiveness of activity trackers with and without incentives to increase physical activity (TRIPPA): a randomised controlled trial. *The Lancet Diabetes & Endocrinology*, *4*(12), 983–995. doi: 10.1016/S2213-8587(16)30284-4

- *Treatment*_j is a dummy variable taking value 0 for households allocated to the control group, and 1 for households allocated to *any* treatment group;
- γ_d is a fixed effect for the day of the week;
- *week*_{*ijd*} is a categorical variable for the (actual) calendar week that the read is recorded;
- baseline_{ijd} is the value of the outcome on the same day of the last week of the baseline period, approximately five months earlier. Missing values for baseline_{ijd} will be coded as -99 to ensure that we include as many participants as possible;

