- *missing. baseline*_{*ijd*} is a dummy variable that equals 1 if *baseline*_{*ijd*} is missing and 0 otherwise and will capture whether MVPA is systematically different for individuals who are missing baseline data for the same day;
- X_{ij} are individual level (including age, sex, ethnicity, education, BMI at baseline, and brand of wearable) and family level covariates we will take missing values for these covariates as separate categories rather than imputing;
- δ_{c_j} are the cluster (i.e. household) level random effects, which have mean zero and follow a normal distribution;
- For each family *j*, $\delta_{p_{ij}}$ are the individual (person) level random effects, which have mean zero within each household and follow a normal distribution;
- u_{ijd} is an idiosyncratic error term. We will use a compound symmetry covariance structure (default for a model with random intercepts).

The primary outcomes for diet are:

- Fruit and vegetables (g/day);
- Fibre (g/day);
- Free sugars (% daily food energy);
- Saturated fat (% daily food energy);

as self-reported in Intake24 recalls at the 5-month follow-up point. We will use a similar model to analyse this outcome, as shown below:

(2)
$$y_{ij} = \alpha + \beta Treatment_{j} + \gamma_{D} weekday_{ij} + \gamma_{W} week_{ij} + \gamma_{N} num. admin_{ij} + \dots \gamma_{B} baseline_{ij} + \gamma_{A} weekday. baseline_{ij} + \gamma_{X} X_{ij} + \delta_{Cj} + u_{ij}$$

$$\delta_{cj} \sim N(0, \sigma_c^2)$$
 for all j; $u_{ij} \sim N(0, \sigma_u^2)$ for all i, j

where:

- y_{ij} is person *i*'s energy intake according to Intake24 surveys at 5 months. If the person took two surveys, we average their reports;
- weekday_{ij} is the proportion of administrations at 5 months that occurred on a weekday (rather than on the weekend). For example, if an individual had one administration on Monday and one on Saturday, weekday. ind_{ij} equals 0.5. This is intended to account for the difference in dietary patterns between

weekdays and the weekend;

- *num. admin*_{ij} is the number of administrations at 5 months (1 or 2);
- baseline_{ij} is calculated in an analogous way to y_{ij}, but for the administration(s) at baseline;
- *weekday.baseline*_{ij} is calculated in an analogous way to *weekday*_{ij}, but for the administration(s) at the baseline;

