The impact of offering incentives (compared to not offering any incentives) on exploratory outcomes at the 5 months mark will be assessed using similar methods as the ones for the primary analysis. We will not impute values at baseline or at 5 months. If there are missing values for an exploratory outcome at baseline, we will add an indicator variable for missingness to the set of covariates so that all individuals with non-missing values for the outcome at 5 months can be included.

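### The dietary primary model has no term for a missing baseline, so, fitted as written, it drops randomised participants whose baseline recalls are all voided, even if their 5-month recalls are valid

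*Protocol*

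**What the plan says.** - **Entry (Protocol 2.2.3).** "Participants cannot complete baselining if they do not respond to at least one 24-hour dietary recall using" Intake24. No quality condition is attached, and "The second intake24 is optional". User C in the Figure 1 illustration (2.2.4) is randomised after one recall.
- **Voiding (2.6.2).** Before analysis, "we will exclude administrations satisfying any of the following conditions": under 10 items, at most three eating occasions, under three minutes to complete, or energy outside 400–4,000 kcal with no explanation from the participant. A second step works on values: "We will then exclude values below the 1st or above the 99th percentile, by gender". Neither step exempts baseline recalls.
- **No imputation (2.6.3.2).** Dietary data are not imputed, whether a user gives one recall or none at a collection point.
- **Diet model (2.6.3.5, equation (2)).** The baseline covariate is built like the outcome, "but for the administration(s) at baseline". The weekday share at baseline is built the same way. No term covers a missing baseline. The separate-category rule for missing covariates applies to the X variables (age, sex, ethnicity and so on).
- **Elsewhere.** For exploratory outcomes, section 2.6.3.10 says: "If there are missing values for an exploratory outcome at baseline, we will add an indicator variable for missingness to the set of covariates". In equation (1) for physical activity, a missing baseline "will be coded as -99 to ensure that we include as many participants as possible", paired with a dummy.
- **Principle (2.6.3.4).** The whole analysis is described as intention to treat.

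**The concern.** The entry condition and the analysis define a usable baseline recall differently. A participant can be randomised on one hurried recall, supply good recalls at 5 months, and still have no value for two covariates in equation (2). A regression fitted in the usual way deletes that row. Because the quality rules act on the whole recall, the person is lost for all four dietary primary outcomes. The percentile trimming acts on single values, so a trimmed baseline value may cost only the outcome concerned.

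At stake are precision on four of the six primary outcomes, the stated intention-to-treat principle, and who remains in the sample: those kept are people who gave at least one full baseline recall. This loss is not in the Table 6 attrition figures. Section 2.4.2.3 defines attrition there as people with no outcome data, and these participants have outcome data.

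**Working it through.** **1. Does the text lead to the loss?** Entry takes one recall of unspecified quality (2.2.3). Recalls are voided afterwards (2.6.2). Nothing is imputed (2.6.3.2). Equation (2) needs a baseline intake and a baseline weekday share and has no missingness term (2.6.3.5). The sentence there that defines remaining variables as in equation (1) does not fill the gap: baseline intake has its own definition under equation (2), and the missing-baseline dummy does not appear in it. The protocol does not state the loss. It follows from fitting the printed model.

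**2. Reproduce the plan's own figure (fruit and vegetables).** Inputs:
- SD 190 g/day (2.4.2.1)
- baseline correlation 0.5 and household ICC 0.3 (2.4.2.2)
- households 39%, 41% and 20% with 1, 2 and 3 adults, and a Bonferroni divisor of 4 for diet (Table 5)
- 2,100 control against 3 × 700 pooled, 80% power (2.4.1)
- overall two-sided alpha of 0.05 (assumed; only the divisor is stated)

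Mean adults per household = 0.39 + 2 × 0.41 + 3 × 0.20 = 1.81. 
Design effect = 1 + (1.81 − 1) × 0.3 = 1.243. 
Alpha = 0.05/4 = 0.0125, so z = 2.498; for 80% power z = 0.842. 
SE = 190 × √[(1 − 0.5²) × 1.243 × 2/2,100] = 5.66 g/day. 
Minimum detectable effect = (2.498 + 0.842) × 5.66 = 18.9 g/day, against 18.7 stated. 
Power for 18.7 g/day = Φ(18.7/5.66 − 2.498) = 79.0%.

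The stated figure is reproduced closely enough to use as the reference.

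**3. Lose a share f of the analysed sample.** The documents give no value for f, so the values below are assumptions. As written, N = 4,200 × (1 − f) and the SE grows by 1/√(1 − f).

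**4. Keep them with an indicator.** People without a baseline have residual variance 1 instead of 1 − 0.5² = 0.75, so each counts as about 0.75 of a person. Effective N ≈ 4,200 × (1 − 0.25f).

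| f (assumed) | As written: N | MDES, g/day | Power for 18.7 | With indicator: effective N | MDES, g/day | Power for 18.7 |
|---|---|---|---|---|---|---|
| 0 | 4,200 | 18.9 | 79.0% | 4,200 | 18.9 | 79.0% |
| 2% | 4,116 | 19.1 | 78.0% | 4,179 | 18.95 | 78.7% |
| 5% | 3,990 | 19.4 | 76.5% | 4,148 | 19.02 | 78.4% |
| 10% | 3,780 | 19.9 | 73.8% | 4,095 | 19.15 | 77.8% |
| 20% | 3,360 | 21.1 | 67.6% | 3,990 | 19.4 | 76.5% |

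The design effect is held at 1.243 throughout. The detectable effect passes the 21 g/day target (2.4.2.1) only at about f = 20%.

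**The case against.** **The loss is inferred, and the SAP may deal with it.** No sentence says such participants are dropped, and handling of a missing covariate is often left to a SAP, which is not among the documents here. It is right that the loss is an inference. But the protocol prints equation (2) term by term and, for other outcomes, does say what happens when a baseline is missing. A gap in a model that has been written out is fair to raise.

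**Equation (1) is a weaker precedent than it looks.** A reader might infer that diet is the odd one out because physical activity keeps everyone through its dummy. The documents do not support that. The dummy marks a missing baseline on the matching day. Users with fewer than 4 valid baseline days are explicitly excluded from the physical activity analysis (2.6.3.2 and the footnote on valid days in 2.2.3). The person-level precedent is section 2.6.3.10. This objection stands.

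**Safeguards exist.** Intake24 prompts on implausible portions and meal gaps, the second recall is encouraged with £5 in points, and one valid recall out of two is enough. The energy rule spares people who report an unusual day or a weight-gain or weight-loss diet. All this lowers the failure rate. None of it applies the item-count, eating-occasion or completion-time rules before randomisation.

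**The size is unknown and probably modest.** People still reporting at 5 months may be more careful than average, and hurried reporters may fail the same rules again at 5 months and be lost anyway. This stands, and it is why the percentages above are only illustrative.

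**Conclusion.** The point holds as a gap in the specification of equation (2). As printed, the model leaves out of all four dietary primary analyses any randomised participant with a valid 5-month recall but no valid baseline recall. Trimming of baseline values may remove others from single outcomes.

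Under an assumed 5–10% loss, power for 18.7 g/day falls by about 2.5 to 5 percentage points (79.0% to 76.5% or 73.8%). An indicator recovers most of this (78.4% or 77.8%). These figures rest on the assumed alpha, on the protocol's ICC and baseline correlation, and on a loss rate that the documents do not give.

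Two stronger readings are tempting and not supported. One is that the dietary treatment comparison is biased: the exclusion depends on data recorded before randomisation, so it does not by itself unbalance the arms. The other is that those lost eat less fruit, vegetables and fibre: this is plausible for people with short recalls, but nothing in the documents shows it.

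**What to change.** In equation (2), when no valid baseline value exists, set the baseline intake and the baseline weekday share to a constant and add a person-level missing-baseline indicator. Define the indicator separately for each outcome, so that a trimmed baseline value is handled in the same way. With the indicator in the model, the choice of constant does not affect the treatment estimate. State that every randomised participant with a valid 5-month recall is analysed, and report by arm how many had no valid baseline. If baseline diet enters the retention model for the inverse probability weights (2.6.3.1), use the same coding there.

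The cost is one model term and a sentence of text. Because the missingness precedes randomisation, the indicator is a sound device here.

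Applying the section 2.6.2 checks when the baseline recall is submitted, with a prompt to repeat a failed one, is optional. It would reduce the problem at source but add burden in a phase that the protocol deliberately keeps light and where it already expects 40% attrition. It would also select careful reporters before randomisation, for the physical activity outcomes too.

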The methods used for the IPE will be (i) rooted in the details of the Theory of Change and the user journey, (ii) mindful of the needs of the research participants, especially those from more deprived communities, and (iii) form part of an integrated plan with the impact evaluation, so that the analysis from the IPE can help to explain any significant or null effects observed. Based on these three principles, the mixed-methods IPE will triangulate findings from qualitative interviews and focus groups and quantitative analyses of in-app data. Comparing and contrasting between these multiple sources of data will allow us to (i) gain insights across a large number of individuals whilst also (2) developing an in-depth understanding of individual experiences.

1. Introduction

Behavioural risk factors represent the largest opportunity to reduce health burdens across the population, making up more than 50% of the preventable Disability Adjusted Life Years (DALYs) as estimated by the Global Burden of Disease study.² Furthermore, behavioural risk factors have a steep social gradient, and are therefore a key contributor to health inequities.

Unhealthy diets and low levels of physical activity are associated with a wide range of chronic conditions, including excess weight, cardiovascular disease, type 2 diabetes, and some forms of cancer.^{3 4} Despite the importance of eating healthily and being physically active, it is estimated that nearly 40% of adults do not reach the recommended 150 minutes of physical activity per week⁵, 72% of adults consume less than five portions of fruit and vegetables per day⁶, and on average adults consume more energy, saturated fat, and sugar than recommended⁷.

In the UK, the Eatwell guide and the Chief Medical Officers (CMO) guidelines for physical activity provide recommendations for how adults can achieve a healthy diet and healthy physical activity levels. To support adults in England to translate these recommendations into practice, the DHSC has decided to pilot an app-based financial incentive scheme to incentivise adults to eat healthier diets and be more physically active. The financial incentive scheme will be piloted in Wolverhampton and its potential effectiveness will be evaluated to inform decisions about whether and how to further scale the intervention.

² Global Burden of Disease Data (link)

³ ibid.

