	Eligibility	Full postcode	Yes	To select eligible participants, and to merge postcode-level deprivation data with GUIDs	N/A
	Eligibility	Resident of Wolverhampton	Yes	To select eligible participants	Yes; No
Uptake and	Wearable use	Daily wear time	Yes	For imputation of missing values	0~24 hours
Engagement	App use	Whether a GUID opens the app by day	Yes	To infer active user status and attrition	Used to identify different types of users: Very active users: app installed and opened at least once over the course of 7 days Active users (Users who have opened the app at least once in the last 30 days). Inactive users (Users who have not opened the app in 30 days)

Table 10. Illustrative structure of data fields to be collected by HUL and to be transferred to BIT

			Churn outs (Users who have not open the app for more than 30 days)
App open date	Yes	To examine wear time / app opens for the same GUID over time	N/A

[figure not shown]

Figure 3. High-level user journey for participants, from an evaluation point of view.

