Adults per household	Number of households	% of total (102,177 households)		
1	39,777	39%		
2	41,784	41%		
3+ *	20,616	20%		
* set to 3 for simplicity in estimations as Census 2011 data does not provide further granularity				

* set to 3 for simplicity in estimations as Census 2011 data does not provide further granularity

Adjusting for multiple comparisons

For the primary outcomes, we will adjust for multiple comparisons using the Benjamini-Hochberg procedure within the physical activity outcomes (2 comparisons) and dietary outcomes (4 comparisons) separately. For the exploratory outcomes and questions, we will adjust for multiple comparisons separately within each research question and separately for physical activity and dietary outcomes. For example, when examining effects after 1 month on the primary outcomes, we will perform 2 comparisons for the physical activity outcomes and 4 for the dietary outcomes. We will do the same for the analysis at 3 months.

Baseline measures and other covariates

We assume that the inclusion of covariates such as baseline calorie intake, baseline MVPA min/day, socio-demographic information, and anthropometric information will reduce variance in the outcome measures, and therefore increase power. Based on prior research, the pre-post correlation in the calorie intake measure using Intake24 is expected to be ~0.5; for the measure of MPVA min/day this is expected to be ~0.8.⁹² Therefore, we conservatively assume that a correlation coefficient of at least 0.5 is realistic in this trial.⁹³

⁹² https://www.ncbi.nlm.nih.gov/pmc/articles/PMC6722486/;

https://journals.humankinetics.com/view/journals/jpah/8/5/article-p668.xml

⁹³ Note that our estimates are additionally conservative because we do not explicitly factor in multiple measurements per participant during both baseline and outcome timepoints (e.g. participants will be asked to complete two Intake24 measurements during baseline, and will be asked to wear the wearable device every day). We have chosen to not factor this in due to the uncertainty around compliance with the Intake24 and daily wearing of the wearable devices.

Appendix C - Recommended dietary intake according to the Recommended dietary intake according to the Government Dietary Recommendations

Outcome	Current intake	Desired change
Carbohydrates	212 g/day	Increase
Free sugars	51 g/day	Reduce
Total Fat	69 g/day	Met
Saturated fat	25 g/day	Reduce
Fibre	18 g/day	Increase

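### The dietary models take baseline diet only from one or two Intake24 recalls; adding matching items from the food frequency questionnaire answered before randomisation is an optional, modest gain in precision

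*Protocol*

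**What the plan says.** Section 2.2.3 sets out the steps before randomisation. At least one Intake24 recall is required, and "The second intake24 is optional; users are encouraged to complete the second one within 3 days". The same list includes a further dietary instrument: "Participants answer a food frequency questionnaire which will be used to create personal diet challenges". It is listed with the baselining steps, not with the optional surveys. The section gives greater precision as the reason for collecting outcome measures at baseline.

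In section 2.6.3.5, equation (2) has one baseline diet term per outcome. It is built in the same way as the follow-up outcome, "but for the administration(s) at baseline", so it is one recall or the average of two. For the other covariates, "we will control for the individual characteristics of age, sex, ethnicity, education, BMI at baseline, the brand of wearable". The definition of X under equation (1), which carries over to equation (2), adds "family level covariates we will take missing values for these covariates as separate categories rather than imputing". No term for the food frequency questionnaire appears in either equation.

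Appendix B states that "the pre-post correlation in the calorie intake measure using Intake24 is expected to be ~0.5", and the power calculation uses a covariate correlation of 0.5.

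**The concern.** A single 24-hour recall is a noisy reading of habitual diet, and with a pre-post correlation of 0.5 it removes only a quarter of the outcome variance (0.5² = 0.25). A questionnaire on usual frequency of consumption may carry information that one or two particular days miss. If it does, and it is left out of the model, some precision is lost on data that participants have already provided.

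The dietary outcomes are where this would count. They set the sample size of 4,200, and their margin is the narrower one. The fruit and vegetable target is 0.11 SD against a stated minimum detectable effect (MDES) of 18.7/190 = 0.098 SD. For MVPA the target is 0.20 SD against 2.4/26 = 0.092 SD.

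**Working it through.** **Inputs from the protocol**
- SD for fruit and vegetables 190 g/day; dietary target 0.11 SD (section 2.4.2.1, Table 5).
- Household ICC 0.3; covariate correlation 0.5 (section 2.4.2.2).
- 2,100 control and 3 × 700 = 2,100 pooled incentive participants; power 80%; Bonferroni over 4 dietary outcomes (Table 5).
- Households of 1, 2 and 3 adults at 39%, 41% and 20%: mean size 0.39 + 0.82 + 0.60 = 1.81.

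**Assumption:** overall two-sided alpha of 0.05, so 0.0125 per dietary outcome. The protocol does not state it.

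**Step 1. Reproduce the plan's figure**

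Design effect = 1 + (1.81 − 1) × 0.3 = 1.243.

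MDES = (2.498 + 0.842) × 190 × √(1.243 × 0.75 × 2/2100) = 18.9 g/day, against 18.7 stated (1.1% higher). Fibre comes to 0.746 against 0.74, free sugars to 0.627 against 0.63, and saturated fat to 0.318 against 0.31. The plan's figures are reproduced closely enough to serve as the base.

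On the same inputs, power at 0.11 SD with 4,200 participants is 88.4%, and about 3,440 participants would give 80%. With a size-weighted cluster size of 2.12 these become 85.7% and about 3,690.

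**Step 2. Add a second baseline measure**

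Let the recall-outcome correlation be 0.5, the questionnaire-outcome correlation *a* and the questionnaire-recall correlation *b*. Then

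R² = (0.25 + a² − 2 × 0.5 × a × b) / (1 − b²)

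and the standard error is multiplied by √((1 − R²)/0.75). Neither *a* nor *b* is in the protocol, so a range is shown. Reduction in standard error:

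| a | b = 0.2 | b = 0.3 | b = 0.4 | b = 0.5 |
|---|---|---|---|---|
| 0.2 | 0.7% | 0.2% | 0.0% | 0.2% |
| 0.3 | 2.8% | 1.7% | 0.8% | 0.2% |
| 0.4 | 6.5% | 4.7% | 3.2% | 2.0% |

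Worked cell, a = 0.4 and b = 0.2: R² = (0.25 + 0.16 − 0.08)/0.96 = 0.344; √(0.656/0.75) = 0.935, a cut of 6.5%. Ten of the twelve cells are below 3.5%. The gain is nil when a = 0.5 × b, that is, when the questionnaire says nothing about the outcome beyond what the recall says.

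**Step 3. Translate to the plan's scale**
- No gain: MDES stays at 18.7 g/day.
- A 3.5% cut: 18.7 × 0.965 = 18.0 g/day.
- A 6.5% cut: 18.7 × 0.935 = 17.5 g/day, equivalent to about 14% more participants (0.75/0.656 = 1.143).

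A favourable case, with the questionnaire as predictive as the recall (a = b = 0.5), gives R² = 0.333, a 5.7% cut and 17.6 g/day, inside the same range.

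**Step 4. Sensitivity to the recall correlation**

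At 0.25, the low end of Table 5, the same grid gives cuts of 0.4% to 7%.

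**The case against.** The strongest case against is that this is a preference. Adjusting each outcome for its own baseline value, measured with the same instrument, is standard and leaves the randomised comparison sound. The sample size never relied on the questionnaire, and all stated targets exceed the stated detectable effects. This stands, and it is why the point is optional.

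It is also fair that little is known about the questionnaire. Its items are described in the delivery partner's design plan, and the fields passed to the evaluator are in a separate data list; neither is shown. Setting challenges is its only stated use, but the protocol does not say that there is no other. Appendix A notes that such questionnaires do not cover everything eaten. A reader might infer that precision is lost on all four dietary outcomes. The protocol does not support that: nothing shows that a challenge-setting questionnaire informs fibre in grams, or free sugars and saturated fat as a share of food energy.

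A reader might also infer that the primary models omit deprivation, since it is not in the named list, the Introduction says that "behavioural risk factors have a steep social gradient", and Table 10 collects postcode "to merge postcode-level deprivation data with GUIDs". The text does not establish this. X already includes unlisted family-level covariates, and the process-evaluation models in sections 4.2.2 and 4.2.3 give deprivation status as the example of that term. Similarly, the retention model in section 2.6.3.1 refers to baseline observables without a closed list, so neither deprivation nor the questionnaire is shown to be excluded from it.

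On the other side, the dietary margin is not unlimited. If 80% of 4,200 (3,360) remain at five months, the level below which section 2.2.3 moves the focus to three months, the fruit and vegetable MDES becomes 18.7 × √(4200/3360) = 20.9 g/day. That equals the target (0.11 × 190 = 20.9), so a free gain in precision would then be useful.

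**Conclusion.** Equation (2) uses only the Intake24 recalls for baseline diet and does not use a dietary questionnaire answered before randomisation. Using matching items would serve the precision aim that section 2.2.3 states.

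The likely benefit is small: a standard error lower by 0 to 6.5%, mostly under 3.5%, and a fruit and vegetable MDES between 17.5 and 18.7 g/day. This rests on assumed questionnaire correlations and on the plan's recall correlation of 0.5, which Appendix B gives for calorie intake and not for the four primary outcomes. Where no item matches an outcome, expect little or nothing.

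This is an optional efficiency gain. It should not be read as an error, as a shortfall in power, or as evidence that deprivation was left out.

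**What to change.** In section 2.6.3.5, pre-specify in X of equation (2), for each dietary primary outcome that has a matching food group, the corresponding baseline questionnaire item or items. Start with fruit and vegetables. Code missing answers as a separate category, as the plan already does for other covariates, and keep the baseline recall term. Where no item matches, leave the model as it is. Add the item or items to the data transfer if they are not already in it.

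The cost is at most one more transferred field, a few extra model terms and a line of protocol text; participants are asked nothing new. Naming deprivation among the family-level covariates could be done in the same edit, as clarification only.
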